A Hybrid Type-I Implementation-effectiveness research design will allow the research team, comprising investigators with expertise in intervention development, efficacy and effectiveness research, and implementation science, to simultaneously investigate the effectiveness of *SAH-C* in a military population while identifying any barriers to implementation that would need to be addressed before *SAH-C* could be successfully implemented on a larger scale. The study site for this proposed effort is Joint Base Lewis McChord, Washington.

The primary hypotheses are that those receiving *SAH-C* will evidence greater reductions in physical and psychological IPV, and greater increases in relationship satisfaction, relative to those receiving *Supportive Prevention* across the follow up time points.

(c) Specific Objectives.

AIM 1: To test the effectiveness of *SAH-C* for military couples on an installation, we will conduct a randomized trial comparing 10 sessions of *SAH-C* to 10 sessions of *Supportive Prevention (SP)* under representative conditions, with 140 couples who are at risk for the development of IPA (risk is established if at least one member of the couple reports at or below a score of 100 on the Dyadic Adjustment Scale (DAS), a cutoff score used to distinguish relationship distress, or they report the presence of psychological aggression in the past three months). This aim will be fulfilled by accomplishing the following subaims:

Subaim 1.1: To compare the frequency of physical IPA perpetration of both members of the couple across conditions as reported by service members and their collateral relationship partners at post-intervention and two 3-month follow ups.

Subaim 1.2: To compare the frequency of psychological IPA perpetration of both members of the couple across conditions as reported by service members and their collateral relationship partners at post-intervention and two 3-month follow ups.

Subaim 1.3: To compare relationship satisfaction across conditions as reported by service members and their collateral relationship partners at post-intervention and two 3-month follow ups.

AIM 2: To explore differences in compliance factors across conditions, we will compare session attendance.

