In total, 28 intervention groups will be conducted (14 for each condition), with five couples per group. Please see Section 2.c. for an initial outline of the *SAH-C* intervention. The *SP* intervention, used in our prior trial, is based on the work of Jennings⁷⁶ and on Yalom's⁷⁷ primary therapeutic factors for group intervention. This intervention involves minimal facilitator-directed intervention beyond encouragement of a mutually supportive environment and focus on relationship issues. In *ST*, the provider will allow group members to set the session agenda and address themes and topics that spontaneously emerge in the group interaction. The provider will emphasize a collaborative group norm and refrain from using active skills-training interventions. The provider will be instructed to address the group as a whole rather than individuals, and use brief verbalizations and nonverbal gestures to stimulate vigorous and helpful group interactions. This intervention was chosen to examine the relative benefits of the cognitive and behavioral interventions used in *SAH-C*.

(d) Intervention Integrity

Intervention integrity for *SAH-C* will be monitored using the intervention integrity measures used during Phase 1, as outlined in Section D.2.5. The same procedure will be used to measure intervention integrity for the *SP* condition, utilizing the modified *SP* codes developed in our previous trial. A framework of adaptations and modifications to evidence-based interventions⁷⁸ will be used to complement the integrity measure and identify any adaptations that the trained psychoeducational facilitator makes within session to address potential challenges or participant needs. Intervention integrity and adaptation data will be examined as implementation outcomes and will also be integrated with qualitative data to understand challenges to delivering the intervention with an adequate level of integrity and perceptions of the effectiveness of any adaptations that are made.

(e) Additional Intervention and Early Termination

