assumed to be a function of observed covariates and previously measured outcomes, but not unobserved outcomes). Based on such considerations, this type of an approach has been recommended for analyzing outcomes in prevention trials as it is generally more powerful than traditional repeated measures analyses of variance.⁹¹ In the current project it is of interest to model person-specific effects (i.e., time course for each participant), as well as the variation of responses between individuals. In addition, because of the suspected intraclass correlation between individuals nested within intervention groups, couples, and perhaps intervention site, these variables will be treated as fixed effects in the analyses. Time will be modeled as a random effect, and condition (*SAH-C* and *ST*) will be a fixed effect. Change in intervention outcomes over time and differences between the conditions over time (intervention by time interactions) will be examined. The primary effect size for the study will be derived from the random regression analyses, and specifically the intervention by time interaction, which will compare the two groups across intervention and follow ups. There are covariates that are *a priori* hypothesized to be associated with intervention outcomes, including socioeconomic status and education, and these will be included in follow-up analyses to significantly reduce error variance.

(e) Exploratory Analyses

Differences between the two group conditions in participant intervention compliance (Aim 2) will be explored by examining condition differences in session attendance using ANOVAs.

(f) Qualitative Analytic Strategy and Data Integration

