Our first consideration in estimating the necessary sample size for detecting differential change over time in *SAH-C* versus *SP* in terms of IPA incidence was the expected incidence rate of IPA during the follow-up period. Our sample is at high risk for such incidence as defined by the presence of high levels of marital distress. While there is no prospective military data available that directly speaks to such incidence rates, available estimates suggest a 33% one-year prevalence of IPA among trauma exposed service members.⁹³ Conservatively, it would be expected that during the current project, approximately 16% of cases of IPA would emerge (half of the one year prevalence). However, inclusion of only couples with high levels of marital distress will increase this estimated incidence rate. Accordingly, we expect an increase of 10% in the incidence rate. Together, we based power analyses on an estimated 26% one-year incidence rate. Our second consideration involved expected sample attrition. Based on our prior trial and the specific plan for data capture outlined for the project, we estimate that about 15% of participants will provide no follow-up assessment data. However, power analyses were conducted based on the conservative estimate of 20% assessment dropout. Consistent with an ITT approach, regardless of intervention dropout, we will assess participants randomized into the trial. Thus, dropout from measurement versus intervention is of greatest concern. Our third consideration involved expected within-subjects correlations. The within-subjects correlation was estimated as the average correlation observed in our previous trial for pre-intervention, post-intervention, and follow-up data on reports of physical and psychological IPA on the Revised Conflict Tactics Scale (CTS-2).⁴⁴ These correlations ranged from .53 to .90. We also considered the expected intra-class (group) correlation, which was approximately .05. Finally, consistent with recommendations,⁹⁴ we considered the intra-class (dyadic) correlation among couples. We did not incorporate an estimate of such correlations into power analyses because of our proposed use of a composite measure of IPA, which results in a single index of IPA, thereby eliminating intra-dyad correlations. Together, we assumed an intra-class correlation of .38 for power analyses. Our fifth consideration involved the expected effect size of the *SAH-C* relative to *ST*. Our prior work suggested an ITT effect size of $d = 1.01$. A conservative estimate of a mean effect size of $d = .5$ for the *SAH-C* in terms of reduction of IPA incidence was utilized for the power analysis.

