
Each of these considerations was used to calculate the needed sample size for testing the main hypotheses in the proposed project. Power analyses were conducted for the main hypothesis tests involving IPA perpetration and were conducted using the GEESIZE Macro in SAS Proc Mixed according to recommendations for estimating sample sizes needed in repeated measures experiments.⁹⁵ Together, assuming (1) 26% incidence of IPA in the control condition, (2) 20% overall attrition, (3) .70 within-subjects correlation, (6) $d = .5$, (5) two-tailed, and (6) $p < .05$, the proposed total N of 280 (140 couples) will provide ample power ($> .9$) to detect differences in IPA frequency across experimental conditions.

(8) Human Studies Section

(a) Risk to Subjects

Human Subjects Involvement and Characteristics

The study population consists of service members attached to an installation who may be at risk for intimate partner aggression (IPA) and their intimate partners. The participants will be 150 service members (10 in Phase 1; 140 in Phase 2) and their partners who will provide data on IPA. The research team has conducted several intervention studies with military samples. There are currently 383 referrals annually to the Family Advocacy Program at Madigan Army Medical Center that do not meet the criteria for domestic abuse, but still require help in working through the various challenges associated with solving differences about money, children, sex, and friends. In addition, there are 4 M&FTs who work full time providing services to couples who have not yet come to the attention of the Family Advocacy Program, Madigan Army Medical Center. These providers average around 210 couples per year each. Thus, there is a pool of more than 1,600 couples who could be referred for *SAH-C* during the recruitment period, which would help us easily meet our recruitment goal.

Inclusion/Exclusion Criteria

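### Intervention group and couple are fixed effects nested in condition, so shared change within groups is left out of the standard error of the primary condition-by-time test

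*Combined protocol and SAP*

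**What the plan says.** Section (7)(d) Primary Data Analyses specifies random-effects regression for the Aim 1 outcomes. It recognises likely correlation and says of "individuals nested within intervention groups, couples, and perhaps intervention site, these variables will be treated as fixed effects in the analyses". Condition is fixed as well. The only random term named is time: "Time will be modeled as a random effect", next to text about each participant's own time course. The primary effect size is "specifically the intervention by time interaction, which will compare the two groups across intervention and follow ups".

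The other relevant statements are:

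- Section (5)(c) Interventions: "In total, 28 intervention groups will be conducted (14 for each condition), with five couples per group".
- Section (7)(g) Power Analysis, on the group correlation: "We also considered the expected intra-class (group) correlation, which was approximately .05". It does not say whether this refers to level or to change.
- Section (7)(g), on the unit for aggression: "our proposed use of a composite measure of IPA, which results in a single index of IPA, thereby eliminating intra-dyad correlations".
- Section (7)(g), on sample size: "the proposed total N of 280 (140 couples) will provide ample power", stated as above .9. The closing list of assumptions does not include the group correlation.
- Section (1)(b), on location: "The study site for this proposed effort is Joint Base Lewis McChord, Washington".

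No section gives a group-by-time term, a cluster-robust variance, or degrees of freedom based on the number of groups.

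**The concern.** Two things follow from the wording.

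First, group and couple are nested in condition. Once their fixed indicators are in the model, condition adds no information and its main effect is aliased.

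Second, and more important, fixed intercepts take out differences in level only. Groups start after baseline, and section (2)(c) chooses a group format because cohesion appears to be linked to prevention, so it is plausible that members of a group change together. With only a person-level (or couple-level) random time slope, the model treats those changes as independent between couples. If they are not, the standard error of the primary interaction is too small and the test rejects too often. For outcomes analysed by person, most clearly the Dyadic Adjustment Scale (DAS), correlation of change between partners is left out too.

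**Working it through.** **1. The plan's own power figure.** Inputs from (7)(g): d = .5, 20% attrition, two-sided .05, 140 couples. Treating 280 × .8 = 224 persons as independent (112 per arm), power is .96, so the stated figure is reproduced. With one index per couple (56 per arm), power is .75 if d is in SDs of change. It is .92 if d is in raw SDs and the .70 within-subject correlation is applied to one follow-up minus baseline (change SD = √(2 × .30) = .775 raw SD). The claim of more than .9 therefore holds under some readings only, before any clustering.

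**2. Aliasing.** Design matrix for 28 groups × 5 couples × 4 time points:

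| Columns in the model | Rank | After adding condition | After also adding condition × time |
|---|---|---|---|
| Group indicators + time | 29 | 29 | 30 |
| Couple indicators + time | 141 | 141 | 142 |

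The main effect adds no rank and is aliased. The interaction adds one and is estimable. Adding fixed group-by-time terms would not help: that matrix has rank 56 and stays at 56 when condition × time is added, so the primary test would be aliased too.

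**3. Type I error of the primary test.** In balanced data the interaction test under the model as written is an unclustered comparison of change. With m units per group:

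- design effect DE = 1 + (m − 1) × ICC of change
- actual error = 2 × [1 − Φ(1.96/√DE)]

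The ICC of change is an assumption. The value .05 is borrowed from (7)(g), and .01 to .10 is shown as a range.

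| Unit | m | ICC of change | DE | Error |
|---|---|---|---|---|
| Couple composite | 5 | .01 | 1.04 | .055 |
| Couple composite | 5 | .05 | 1.20 | .074 |
| Couple composite | 5 | .10 | 1.40 | .098 |
| Couple composite, 20% attrition | 4 | .05 | 1.15 | .068 |
| Person | 10 | .05 | 1.45 | .104 |

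For the third-last composite case in numbers, ICC .05 with m = 5: 1 + 4 × .05 = 1.20; 1.96/√1.20 = 1.789; error .074. Null simulations gave .073 for this case, .066 to .067 with 4 couples per group, and .102 to .104 at person level. Comparing the 28 group means on 26 degrees of freedom gave .048 to .051.

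For persons, partner correlation of change r adds to this: DE = 1 + r + 8 × ICC. The documents give no value for r. At ICC .05, r = .05 (no more than group-mates) gives 1.45 and .104; an assumed r = .38 gives 1.78 and .142.

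**4. Dependence on when the group effect acts.** If it is a constant shift in level present from baseline, the composite test keeps its size (simulated .049 to .051). If it begins after baseline with ICC .05 on the follow-up score, and within-subject correlation is .70, simulated error is .083 for a slope test and .105 for mean follow-up minus baseline.

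**5. Power once group change is in the error term** (d = .5, 20% attrition, ICC .05, 26 degrees of freedom, 4 couples per group; DE 1.15 for couples, 1.35 for persons):

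| Unit and scale of d | Unclustered | Clustered |
|---|---|---|
| Composite, SDs of change | .75 | .66 |
| Composite, raw SDs | .92 | .87 |
| Person, SDs of change | .96 | .87 |
| Person, raw SDs | .998 | .98 |

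With r = .38 assumed, the person-level DE is 1 + .38 + 6 × .05 = 1.68, and power is .79 (SDs of change) or about .95 (raw SDs).

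**The case against.** **The aliased main effect is not the primary test.** This stands. Aliasing shows that the model is misdrafted; it does not bias the interaction.

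**The inflation rests on a quantity that the documents do not give.** This also stands. The .05 is not labelled as level or change, and the supportable results run from no inflation to about .10 for the composite. The figure of about 7% is one conditional point in that range.

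**Fixed may be a slip for random.** Section (7)(d) does call for random-effects regression. If time were also random at group level, most of the concern would be met. But the section ties random time to each participant's course and names no group-level slope, and random group intercepts alone would still leave shared change out. On this reading the text needs correcting all the same.

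**The .38 has no basis as a partner correlation.** Section (7)(g) gives .38 without saying what it measures, just after stating that dyadic correlation was not built into the power analysis. It is used above only as an assumed upper illustration, and the conclusion does not need it.

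**Physical aggression is not covered by these figures.** Correct. They are normal-theory results, and that outcome is highly skewed (Table 1 in (3)(a) has a baseline mean of .14 with SD .48 in one arm).

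**Conclusion.** The concern holds. As written, the model cannot estimate the condition main effect; this is exact and needs no assumption. It also omits group-level variation in change from the standard error of the primary interaction. The size of the resulting error is conditional: about .074 for the couple composite if the ICC of change is .05 with five couples per group, .055 to .098 for ICC .01 to .10, and nominal if group effects are constant from baseline. Person-level outcomes are affected more, at about .104 for ICC .05 before any extra correlation between partners. The stated power above .9 depends on the unit of analysis and the scale of d, and for the composite it falls below .9 on both scales at ICC .05. Because this is the prespecified primary model, it should be corrected before outcome data are analysed.

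**What to change.** In section (7)(d), replace the sentence that makes group, couple and site fixed with wording such as:

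> Intervention group will be a random effect with a random intercept and a random group-by-time term (or inference will use cluster-robust standard errors by group with a small-sample correction). For outcomes analysed by person, such as the DAS, couple will also have a random intercept and slope, or partners will have a dyadic covariance. Condition, time and condition-by-time will be fixed, with a random time slope for the unit analysed. Degrees of freedom for condition-by-time will be based on the 28 groups (about 26).

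Choose one of the two variance approaches in advance. State for each Aim 1 outcome whether the unit is the couple composite or the person, since (7)(g) describes a composite but counts 280. Remove intervention site, as only one installation is named. Restate power in (7)(g) under this model, with the unit, the scale of d and the ICC of change made explicit.

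The cost is text, a few lines of model code and some precision; conduct and data collection do not change. At ICC .05 with full groups the standard error rises by about 10% for the composite (√1.20 = 1.095; 2% to 18% for ICC .01 to .10) and about 20% at person level (√1.45 = 1.204). The loss of power is as tabulated above.

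### If both partners' DAS scores enter one model, fixed couple effects leave their shared change unmodelled, and the primary condition-by-time test of relationship satisfaction exceeds its nominal 5% level.

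*Combined protocol and SAP*

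**What the plan says.** Section (1)(b) lists three primary hypotheses: reductions in physical IPV, reductions in psychological IPV, "and greater increases in relationship satisfaction, relative to those receiving" the comparator. Subaim 1.3 in (1)(c) is "To compare relationship satisfaction across conditions as reported by service members and their collateral relationship partners", so each couple supplies two DAS scores per visit.

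Section (g) Power Analysis considers the correlation between members of a couple and leaves it out: "We did not incorporate an estimate of such correlations into power analyses". The reason given is "our proposed use of a composite measure of IPA, which results in a single index of IPA, thereby eliminating intra-dyad correlations". That reason concerns IPA. No composite is stated for the DAS.

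Section (d) Primary Data Analyses puts IPA and relationship satisfaction through the same random-effects regression. It expects correlation among individuals "nested within intervention groups, couples, and perhaps intervention site, these variables will be treated as fixed effects in the analyses". It adds that "Time will be modeled as a random effect", having just said that the interest lies in person-specific effects, meaning a time course for each participant. Condition is a fixed effect, and the primary effect size comes from the intervention-by-time interaction. The section states no couple-by-time term and no residual correlation between partners. It does not say whether the two roles' DAS scores share a model.

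**The concern.** A fixed couple effect is a constant for each couple. It absorbs how satisfied the couple is on average and then cancels from any measure of change, yet the primary test is on change. Partners attend the sessions together, practise skills together between sessions (section (2)(c)) and rate the same relationship, so it is reasonable to expect their DAS scores to move together. If both are in the model and only each person has a random time course, a couple that improves together counts as two independent improvements. The standard error of the condition-by-time effect is then too small, its interval too narrow, and one of the three primary hypotheses is tested above its nominal level.

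A second consequence needs no assumption about correlation. Both members of a couple are in the same condition, so a full set of couple indicators reproduces the condition indicator exactly. The condition main effect that (d) lists cannot then be estimated. The condition-by-time interaction still can.

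**Working it through.** **The plan's own figure.** Section (g) states power above .9 for IPA, with N = 280 (140 couples), d = .5, two-sided .05 and 20% attrition. Counting persons, 280 × .8 / 2 = 112 per arm gives power .963, so the inequality reproduces. Counting couples, 56 per arm gives .754 at one time point, and .927 on a change score using the plan's within-subject correlation of .70. These are IPA figures. The plan states no power or error calculation for the DAS.

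**Inputs for the DAS check**
- From the documents: 140 couples, two reporters per couple, condition constant within a couple, primary test condition by time, two-sided .05.
- Not in the documents: the within-couple correlation of DAS change, ρ. It is an assumption here and is shown over .1 to .8.

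**Derivation.** With balanced data, a test with person-level random slopes and fixed couple intercepts amounts to a two-sample comparison of person slopes, because the couple intercepts drop out of the slopes. With two partners per couple, the true variance of an arm's mean slope is (1 + ρ) times what an independence calculation gives. Hence

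- standard error understated by a factor √(1 + ρ);
- actual type I error = 2 × [1 − Φ(1.96 / √(1 + ρ))].

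| Assumed ρ | SE factor | Type I error, complete pairs | Type I error, independent 20% loss |
|---|---|---|---|
| .1 | 1.05 | 6.2% | 5.9% |
| .3 | 1.14 | 8.6% | 7.8% |
| .5 | 1.22 | 11.0% | 9.8% |
| .7 | 1.30 | 13.3% | 11.7% |
| .8 | 1.34 | 14.4% | 12.6% |

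The error reaches 10% when 1 + ρ = (1.960 / 1.645)² = 1.42, that is ρ = .42.

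The last column takes the plan's 20% attrition and assumes that partners are lost independently of each other. The share of couples with both partners observed is .8² = .64, and with one observed 2 × .8 × .2 = .32. The size-weighted mean number per couple is (.64 × 4 + .32 × 1) / 1.6 = 1.8, so the variance factor is 1 + .8ρ. If partners drop out together, the complete-pairs column stands.

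**Simulation.** 140 couples, four waves, couple intercepts absorbed, 20,000 replicates. Person-level error was 7.5%, 9.1%, 11.0% and 13.3% at ρ = .2, .38, .5 and .7, against 7.4%, 9.5%, 11.0% and 13.3% from the formula. When only the underlying slopes were correlated and the visit-level errors were independent between partners, the error was lower: 9.9% at .5 and 11.9% at .7. With the couple as the unit of change, it was close to 5% in every setting (4.7% to 5.2%).

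**The case against.** The strongest objection is that the plan never says the roles are pooled. Subaim 1.3 names both reporters without saying that their scores share a model. The sponsor's earlier results keep the roles apart: Table 2 in (3)(a) has separate DAS rows for Veterans and partners, and Table 1 has separate tests for Veteran- and partner-perpetrated IPA. Section (5)(a) calls the Phase 2 design analogous to the earlier trial. With one model per role there is no within-couple inflation. This stands as a possibility, but pooling is the better reading. Section (d) nests individuals within couples, and a couple term would serve no purpose in a model holding one person per couple. Since IPA is a single index per couple, the DAS is the primary outcome for which such a term has a use.

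It can also be said that the level at which time is random is not stated, so a couple-level slope might be intended. The only description given, a time course for each participant, points to the person.

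Two stronger readings are tempting, and the documents do not support them:
- A reader might infer that the DAS test treats 280 people as independent. The 280 belongs to the IPA power statement, and the plan does put couple in the model. Only the partners' changes go uncorrelated.
- A reader might infer that the false-positive rate doubles. That needs ρ near .4 and complete pairs, and no value is given. Section (g) does mention an intra-class correlation of .38, which would give 9.5%. It is not described as a partner correlation of DAS change, and the same paragraph says that dyadic correlation was left out.

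**Conclusion.** The concern holds conditionally. The plan's reason for setting partner dependence aside covers IPA and not the DAS, and the couple term that it specifies does not deal with shared change. If both partners' DAS scores are pooled, the condition-by-time test is anti-conservative: about 6% to 14% instead of 5% for assumed ρ of .1 to .8 with complete pairs, and about 6% to 13% if partners drop out independently. These figures rest on balanced data and on ρ as the correlation between partners' observed changes; independent measurement error pulls that below the correlation of their true changes. If the roles are analysed separately, this inflation is absent. Under the stated fixed couple effects the condition main effect is inestimable for any ρ, but this does not remove the primary test. The plan should be corrected because a primary outcome is affected and the remedy is cheap.

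**What to change.** In (d) Primary Data Analyses, state the unit of analysis for the DAS and choose one of two routes.

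1. **Pooled model.** Replace the fixed couple effects with a couple-level random intercept and random change, or let residuals correlate between partners at each visit. Include role (service member or partner) as a fixed factor, and estimate condition by time averaged over partners.
2. **Separate models.** State that service-member and partner DAS scores are analysed separately by role.

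A couple-mean DAS, one record per couple per visit, is equivalent to the first route only when both partners are observed at each visit; otherwise the mean mixes roles.

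The cost is SAP wording and minor model code, plus a wider DAS interval under the pooled model. Recruitment and data collection do not change.

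This does not settle shared change within intervention groups, which is a separate issue. As an illustration, suppose the plan's group correlation of about .05 applied to change, with ten persons per group and ρ = .38. The full variance factor would be 1 + .38 + 8 × .05 = 1.78. Once the couple part is handled, 1.78 / 1.38 = 1.29 remains, which gives a type I error of about 8.4%.
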